11.3.2 Brain metastasis size evaluation

The treating radiation oncologist will measure and calculate the volume for each brain metastasis identified as a contrast enhancing mass on MRI at baseline using radiation oncology treatment planning software. This value will be recorded on the baseline form and every subsequent follow-up form. The appearance (yes/no) of any new brain metastases will be recorded on all follow-up forms.

11.3.3 Lesion response evaluation

Each treated lesion will have a volumetric measurement made at each study imaging follow-up using the visit high resolution MRI scan and radiation oncology treatment planning software. Percentage change in volume from the original baseline volume will be calculated using the formula: [original volume – current volume] / original volume. Lesions with complete resolution will be noted as complete response (CR).

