2.0 OBJECTIVES

2.1 Primary Objectives

- 2.1.1 To determine the feasibility of treating brain metastasis patients with whole brain radiation and simultaneous focal boost using an RA technique. (see Section 11.4)
- 2.1.2 To determine the locoregional control [at visible lesion(s) and new site(s)] in the brain of patients treated with a concomitant boost RA plan.

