11.3.4 Definition of CNS progression

CNS progression will be defined as a > 25% increase in volume for any tracked brain metastasis, or the appearance of any new brain metastasis on a follow-up MRI. For lesions smaller than 1 cm in maximum diameter, a maximum increase of 50% in volume will be necessary to score as progression. This caveat is included to account for potential variability in measurement, which will be most susceptible to proportionate errors at smaller sizes. For greater than 1 cm lesions, the definition will use a 25% rule for change.

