13.0 STATISTICAL CONSIDERATIONS

13.1 Study endpoints

13.1.1 Primary endpoints

- Feasibility – Measurement of the amount of time required for daily treatment
- Rates of toxicities
- Local brain control
- Regional brain control

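### In 11.3.4 the rule for lesions under 1 cm sets a ceiling where a threshold is meant, and the percentage change in 11.3.3 has the opposite sign to the progression rule

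*Combined protocol and SAP*

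**What the plan says.** Section 11.3.3 (Lesion response evaluation) has each treated lesion measured volumetrically at each study imaging follow-up and defines the derived quantity: "Percentage change in volume from the original baseline volume will be calculated using the formula: [original volume – current volume] / original volume". The only outcome named there is complete response.

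Section 11.3.4 (Definition of CNS progression) gives the general rule in words: "CNS progression will be defined as a > 25% increase in volume for any tracked brain metastasis, or the appearance of any new brain metastasis". It then makes an exception: "For lesions smaller than 1 cm in maximum diameter, a maximum increase of 50% in volume will be necessary to score as progression". The reason follows: "This caveat is included to account for potential variability in measurement, which will be most susceptible to proportionate errors at smaller sizes". The section closes with: "For greater than 1 cm lesions, the definition will use a 25% rule for change".

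Section 11.3.4 does not cite the 11.3.3 formula. It does not say whether the 1 cm class is judged at baseline or on the scan being read, and a lesion of exactly 1 cm falls in neither class.

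Section 2.1 makes this a primary objective: "To determine the locoregional control [at visible lesion(s) and new site(s)] in the brain of patients treated with a concomitant boost RA plan". Section 13.1.1 lists "Local brain control" as a primary endpoint without defining its event. Section 13.3 analyses local control by Kaplan-Meier, and Section 12.2 makes local CNS progression an off-study criterion.

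**The concern.** There are three separate defects in adjoining rules.

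- **Ceiling for a threshold.** A maximum is an upper limit. The reason given, that proportionate error is larger in small lesions, calls for a higher minimum than 25%.
- **Sign.** What 11.3.3 calls a percentage change is positive for shrinkage and negative for growth. The last sentence of 11.3.4 speaks of a 25% rule for change, and the only change the protocol defines is the 11.3.3 quantity.
- **Size class.** A lesion just under 1 cm can cross 1 cm as it grows. If the class follows the current scan, its threshold drops from 50% to 25% on the very scan being judged.

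No other lesion-growth criterion exists in the documents, so whoever derives local control will in practice turn to 11.3.4. With 18 patients (Section 13.2), one patient classified wrongly moves a crude local-control proportion by 1/18 = 5.6 percentage points. The documents do not allow an estimate of how many patients would be affected.

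**Working it through.** The plan states no figure to reproduce here. The check applies its rules to example lesions.

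**1. Sign of the 11.3.3 quantity.** Take a baseline volume of 1.00 cc. As written, the value is (original - current)/original. The conventional change is (current - original)/original.

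| Follow-up volume (cc) | 11.3.3 as written | Conventional change | 11.3.3 value above 25%? |
|---|---|---|---|
| 1.30 | -30% | +30% | no |
| 1.50 | -50% | +50% | no |
| 3.00 | -200% | +200% | no |
| 0.70 | +30% | -30% | yes |
| 0.00 | +100% | -100% | yes |

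A cut-off of more than 25% placed on the 11.3.3 value would flag shrinkage and miss growth. The same cut-off applied to an increase, as the first sentence of 11.3.4 words it, classifies every row correctly for a lesion over 1 cm.

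**2. Lesions under 1 cm.** The literal reading combines the opening requirement (more than 25%) with the stated maximum (50%). The intended reading is a threshold of 50%.

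| Growth | Literal: above 25%, at most 50% | Threshold: more than 50% |
|---|---|---|
| 10% | no | no |
| 26% | progression | no |
| 40% | progression | no |
| 50% | progression | no (yes if at least 50% is meant) |
| 51% | no | progression |
| 60% | no | progression |
| 100% | no | progression |

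Above 25% the two readings give opposite answers in every row, except that the answer at exactly 50% depends on whether more than or at least is meant.

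**3. Size class.** Assume spherical lesions, so volume scales with the cube of diameter. This is my assumption; the plan measures volume directly.

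- Growth from 9.0 to 10.1 mm: (10.1/9.0)^3 = 1.413, a 41% gain. Classed by current size (25% rule) this is progression. Classed by baseline size (50% threshold) it is not.
- Lower edge of the disputed range: 1.50^(1/3) = 1.145, and 10/1.145 is about 8.7 mm. A lesion below that at baseline has already gained more than 50% by the time it reaches 10 mm, so both classes agree.
- Upper edge: 10 mm, where the baseline class itself changes.

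The disputed cases are therefore baseline diameters of about 8.7 to 10 mm with growth between 25% and 50%.

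**The case against.** The strongest reply is that a sensible reader would go wrong on none of this. Section 11.3.4 states its main rule in words, as an increase, and does not refer to 11.3.3. A reduction-positive measure suits a section on response, where complete resolution is +100%. No program or database check on the 11.3.3 value appears anywhere in the documents; the treating radiation oncologist measures the volumes, the baseline value is carried on every form (11.3.2), and progression can be judged from the volumes themselves. In the small-lesion sentence, the idea that the increase is necessary for scoring is threshold language, and the next sentence makes the intent plain. The size-class range is narrow, and the entry MRI need only have 5 mm resolution (4.1, 6.1.3), so a contrast of 9.0 with 10.1 mm is finer than that minimum supports.

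Much of this stands. The sign is a labelling fault that causes harm only if cut-offs are applied to that value. The intent of the small-lesion rule can be recovered. The size-class gap is a narrow one, although 11.3.3 calls for high-resolution MRI at follow-up without giving a figure.

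What does not stand is the inference that no correction is needed. An endpoint rule should be right as written, and the closing sentence of 11.3.4 does invite use of the 11.3.3 change. Reading for intent does not settle the size class, because baseline and current size are both reasonable readings.

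A reader might also go further and infer that small stable lesions would be scored as failures. The documents do not support that: the section opens by requiring more than 25% growth for any tracked lesion, so growth of 10% does not score even under the literal reading.

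**Conclusion.** The point holds, within limits. For lesions under 1 cm, the progression rule is wrong as literally written and reverses its own rationale above 25% growth. The 11.3.3 quantity is mislabelled: it is a percentage reduction, opposite in sign to the rule in the next section, and it misclassifies lesions only where the 25% or 50% cut-off is applied to it. The size class is undefined in a way that changes the result for baseline diameters of about 8.7 to 10 mm, assuming spheres.

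A reader might infer that the criterion for the primary local-control endpoint is wrong as a whole. The documents do not support that. The worded rule, "CNS progression will be defined as a > 25% increase in volume for any tracked brain metastasis", works for lesions over 1 cm. Section 11.3.4 also defines CNS progression, which combines lesion growth with new metastases, and nothing in Sections 2.1, 12.2 or 13 names it as the local-control event. The link to local control is an inference, resting on 11.3.4 being the only lesion-growth criterion available.

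No sample-size figure depends on this. Confidence in the textual errors is high; how often they would change a result cannot be estimated from the documents.

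**What to change.** 1. In 11.3.4, for lesions under 1 cm, replace the maximum of 50% with an increase of more than 50%. This matches the strict inequality used for 25% and settles the case of exactly 50%.
2. In 11.3.3, define change as 100 x (current volume - original volume)/original volume, so that growth is positive. Alternatively, keep the formula and call it percentage reduction.
3. In 11.3.4, state that the size class is set by the baseline maximum diameter for the whole of follow-up, with exactly 1 cm in the 25% class.

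A further sentence saying which part of 11.3.4 is the local-control event would make the link to Section 13.1.1 explicit.

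The cost is wording in two subsections and the calculation field on the follow-up form. If the formula is changed rather than relabelled, values already recorded can be sign-flipped. The one drawback is that fixing the class at baseline may call progression slightly later for lesions just under 1 cm than classing them by current size would.

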11.3.4 Definition of CNS progression

CNS progression will be defined as a > 25% increase in volume for any tracked brain metastasis, or the appearance of any new brain metastasis on a follow-up MRI. For lesions smaller than 1 cm in maximum diameter, a maximum increase of 50% in volume will be necessary to score as progression. This caveat is included to account for potential variability in measurement, which will be most susceptible to proportionate errors at smaller sizes. For greater than 1 cm lesions, the definition will use a 25% rule for change.

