1.0 INTRODUCTION/BACKGROUND

Brain metastases are the most common adult intracranial tumor, occurring in approximately 10% to 30% of adult cancer patients, and represent an important cause of morbidity and mortality in this population.¹ The risk of developing brain metastases differs with different primary tumor histologies, with lung cancer accounting for approximately one half of all brain metastases.² The prognosis of patients with brain metastases is poor. The median survival time of untreated patients is approximately 1 month.³ With treatment, the overall median survival time after diagnosis is approximately 4 months.⁴ The RTOG recursive partitioning analysis (RPA) describes three prognostic classes, defined by age, Karnofsky Performance Score (KPS), and disease status.⁵ The most widely used treatment for patients with multiple brain metastases is WBRT. The appropriate use of WBRT can provide rapid attenuation of many neurological symptoms, improve quality of life, extend median survival, and be especially beneficial in patients whose brain metastases are surgically inaccessible or when other medical considerations preclude surgery.^{6,7} The use of adjuvant WBRT after resection or stereotactic radiosurgery (SRS) has been proven to be effective in terms of improving local control of brain metastases, and thus, the likelihood of neurological death is decreased.⁸

The majority of patients who achieve local tumor control die from progression of extracranial disease, whereas the cause of death is most often due to CNS disease in patients with recurrent brain metastases.^{7,8} Currently, no consensus on the optimal radiation schedule for patients with brain metastases is established. Standard treatment regimens include dose fractionation schemes evaluated in the early RTOG studies and range from 20 Gy in 5 fractions to 40 Gy in 20 fractions. The exact regimen used is generally at the discretion of the treating physician and often depends upon issues such as the severity of CNS symptoms, the extent of systemic disease, and physician preference.

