This previous version of this study was a phase I dose escalation trial giving 25 Gy in 10 fractions to the whole brain with simultaneous infield boost (SIB) to a total of 45 Gy in 10 fractions to gross brain metastatic disease. Prior to this, patients were enrolled onto one of two cohorts with whole brain dose of 30 Gy in 10 fractions with SIB to total of 45 Gy in 10 fractions to gross brain metastatic disease or whole brain dose of 37.5 Gy in 15 fractions with SIB to total of 52.5 Gy in 15 fractions to gross brain metastatic disease. A total of 12 patients have been previously enrolled on this trial. No patients have experienced a dose limiting toxicity (grade 3 or above) at least possibly due to study therapy. Also, no patients experienced local brain failure/progression at a site of treated metastatic brain disease. Based on this, we no longer feel that dose escalation to the gross brain disease is warranted and would proceed with a single arm pilot study treating patients with 25 Gy in 10 fractions to the whole brain with simultaneous infield boost (SIB) to a total of 45 Gy in 10 fractions to gross brain metastatic disease.

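### Section 11.3.4 names no reference volume for progression; read with 11.3.2–11.3.3 it is the original baseline, so a treated lesion that shrinks and regrows counts as locally controlled until it exceeds 1.25 × (1.50 × if under 1 cm) its original volume

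*Combined protocol and SAP*

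**What the plan says.** Section 11.3.4 is the only rule for failure of a treated lesion: "CNS progression will be defined as a > 25% increase in volume for any tracked brain metastasis". Any new metastasis also counts. For lesions below 1 cm in maximum diameter, "a maximum increase of 50% in volume will be necessary to score as progression"; the reason given is that measurement variability is "most susceptible to proportionate errors at smaller sizes". Neither threshold is tied to a reference volume, and the scan at which the 1 cm class is judged is not stated.

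Section 11.3.3, immediately before, does name a reference: "Percentage change in volume from the original baseline volume will be calculated using the formula", the formula being "original volume – current volume] / original volume". Section 11.3.2 has the baseline volume entered on the baseline form and on every follow-up form. A smallest or previous volume is not mentioned as a reference anywhere. Section 11.3.3 labels complete resolution as complete response, and no section says how a lesion that later reappears is scored.

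Local brain control is a primary endpoint (13.1.1). Local control and progression-free survival (PFS) are analysed by Kaplan-Meier and compared with published results (13.3). Local CNS progression is an off-study criterion (12.2).

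**The concern.** A reader of 11.3.4 has to infer the reference volume. The natural inference, from 11.3.2 and 11.3.3, is the original baseline. A lesion that responds well and then regrows steadily is then scored as controlled all the way back to its starting size and a quarter beyond. The better the initial response, the more regrowth is tolerated.

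This bears on a primary endpoint and, more weakly, on PFS, where deaths and new lesions also count as events. It also bears on the historical comparison in 13.3, because the reference volumes used in those series are not stated.

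Three gaps in the same rule add to the uncertainty:

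- The 11.3.3 formula is positive for shrinkage, so growth comes out negative, while 11.3.4 speaks of an increase.
- The 50% figure is called a maximum where a minimum must be meant.
- Regrowth at a complete-response site could be read in two ways that give different answers.

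**Working it through.** The plan gives no figure of its own to reproduce here: no target control rate, and no shrinkage, regrowth or measurement-error rate. The check therefore compares thresholds.

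**Inputs.** Thresholds f = 1.25, or 1.50 under 1 cm (11.3.4). Baseline volume V0 (11.3.2–11.3.3). Smallest recorded volume Vmin = (1 − s) × V0, where s is the fraction of shrinkage; s is varied because the documents do not give it.

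**Rules.** Baseline reference: progression when V > f × V0. Nadir reference: progression when V > f × Vmin. The fold regrowth from nadir needed under the baseline reference is f/(1 − s). The extra growth compared with a nadir reference at the same f is log2[1/(1 − s)] volume doublings.

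| Shrinkage s | Fold regrowth, f = 1.25 | Fold regrowth, f = 1.50 | Extra doublings |
|---|---|---|---|
| 50% | 1.25/0.50 = 2.5 | 1.50/0.50 = 3.0 | 1.0 |
| 75% | 1.25/0.25 = 5.0 | 1.50/0.25 = 6.0 | 2.0 |
| 90% | 1.25/0.10 = 12.5 | 1.50/0.10 = 15.0 | 3.3 |

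**Example (sphere, volume = π/6 × d³, class fixed at baseline).** A 2 cm lesion is 4.19 cc. Shrunk by 90% it is 0.42 cc (9.3 mm). Back at 2 cm, the 11.3.3 formula gives 0% change. The baseline reference scores it only above 1.25 × 4.19 = 5.24 cc (21.5 mm). A nadir reference scores it above 1.25 × 0.42 = 0.52 cc (10.0 mm).

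**Direction.** Vmin ≤ V0, so with f fixed, f × Vmin ≤ f × V0. Every baseline-rule progression is also a nadir-rule progression, no later, and never the reverse. Local control under the baseline reference is therefore equal or higher. The order can reverse only if the size class is judged at nadir: 1.50(1 − s) > 1.25 needs s < 1/6 (16.7%), and a nadir below 10 mm then needs a baseline diameter from 10.0 to 10/(5/6)^(1/3) = 10.6 mm.

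**Illustration of size, on assumptions only.** Assume 30% of lesions regrow, nadir at 2–9 months, mean nadir 0.3–0.7 of baseline, doubling time 2–4 months, the protocol's MRI schedule, and no deaths. Simulated 12-month local control was 0.71–0.91 with the baseline reference and about 0.70 with the nadir reference, a difference of about 0.01 to 0.21. By 24 months the difference was at most 0.02. None of these inputs comes from the documents.

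**Complete response.** Here Vmin = 0 and a percentage of nadir is undefined. If reappearance is regrowth of a tracked lesion, the baseline reference requires more than 1.25 × (1.50 ×) the original volume. If it is a new metastasis, it is CNS progression at once, but not clearly local failure. Section 1.0 ties local failure to the sites of treated disease, and 2.1.2 separates visible lesions from new sites. Both suggest that such regrowth is local; neither settles it.

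**Noise under a nadir reference.** Assume log-normal volume error, a lesion truly stable at half its baseline volume, five MRIs to 12 months and the 25% rule. Rates are per lesion.

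| Assumed volume CV | Falsely scored, single scan | Falsely scored, persisting on next MRI | Baseline reference |
|---|---|---|---|
| 5% | 0.7% | < 0.1% | about 0% |
| 10% | 34% | 6.5% | about 0% |
| 15% | 63% | 21% | about 0% |

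The rule fires on any tracked lesion, and 3.1.6 admits up to ten. If lesions err independently, the 6.5% becomes 1 − 0.935^5 = 29% of patients with five lesions and 1 − 0.935^10 = 49% with ten.

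**The case against.** The strongest reply is that the reference is already supplied: 11.3.3 says baseline, 11.3.2 carries it forward, and nothing in the documents calls for a nadir. Section 11.3.4 openly worries about measurement variability, and a baseline reference is robust to it. In the 2 cm example a nadir rule would call progression on a diameter change of 0.7 mm (9.3 to 10.0 mm). Volumes are recorded at every study MRI, so a nadir analysis can be computed from data collected under a baseline rule. The reverse is not true, because local progression takes a patient off study. This is also an 18-patient pilot with no decision threshold.

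Most of this stands, and it decides the form of the remedy. It does not remove the point: 11.3.4 still names no reference, and on the baseline reading it still scores a lesion that has regrown tenfold as unchanged.

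Two stronger readings are tempting. One is that the nadir must become the operating rule. The documents do not support that, given the false-scoring rates above and the effect on follow-up through 12.2. The other takes the statement in 1.0, "With treatment, the overall median survival time after diagnosis is approximately 4 months", and argues that many patients would die before a delayed progression could be scored, so that this share measures the bias. It does not. Doubling times would have to be assumed, the median is not specific to patients entering with KPS ≥ 70, and if deaths are censored and independent of regrowth, the share dying is not the bias in a Kaplan-Meier curve.

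**Conclusion.** The concern holds as a defect of definition with a known direction. It rests on reading 11.3.4 with 11.3.2–11.3.3. That is an inference, though the natural one; a nadir or previous-scan reading is not excluded, and in that case the reference for a primary endpoint is simply undefined. On the baseline reading, regrowth of 2.5-, 5- or 12.5-fold from nadir is tolerated after 50%, 75% or 90% shrinkage under the 25% rule. With the size class fixed, local control is equal to or higher than under a nadir reference.

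The size of the effect on the control rate cannot be derived; the 0.01–0.21 range at 12 months is illustration only. Only treated lesions that shrink first are affected.

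A reader might also infer that the comparison in 13.3 is biased in the trial's favour, or that the phase I statement that "no patients experienced local brain failure/progression at a site of treated metastatic brain disease" is an artefact of the rule. The documents support neither: they do not give the rules of the historical series, and they report no lesion volumes for those 12 patients. This should be fixed, but it does not invalidate the design.

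**What to change.** 1. In 11.3.4, state the reference volume and define increase = (current − reference)/reference × 100, so that growth is positive.
2. Replace the maximum-increase wording with an increase of more than 50%, and fix the under-1 cm class at the baseline MRI. This also removes the reversal.
3. Count reappearance at a treated complete-response site as local failure.
4. Report local control and PFS under both the baseline reference and the nadir reference (smallest recorded volume, baseline included). Baseline as the operating rule, with nadir as a pre-specified sensitivity analysis, is acceptable. If nadir is made the operating rule, 11.3.4 and 12.2 must be reconciled, because earlier scoring would otherwise shorten follow-up. Show the nadir result also with persistence on the next MRI where one is available.
5. For each historical series compared under 13.3, state its progression rule.

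The cost is protocol wording and one extra analysis; no new scan or measurement is needed, since 11.3.3 already has every treated lesion measured at each study MRI. The downsides are that local control may look worse under the nadir version, and that this version is more exposed to measurement noise, which compounds across lesions, and to radiation necrosis (listed as a late effect in 6.5.2), which persistence may not separate from regrowth.
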